### **4. GENERAL STATISTICAL CONSIDERATIONS**

Analyses described in this SAP will be conducted separately for each of the two cohorts. Treatment comparison will be primarily between each of the KPL-301 treatment arms (10 mg/kg, 6 mg/kg) vs placebo. Comparisons between the pooled KPL-301 treatment arms vs placebo will also be provided.

Summary statistics for continuous variables will include n (non-missing observations), mean, standard deviation, minimum, median, and maximum. Summary statistics for categorical variables will be presented in terms of frequencies and percentages based on the analysis set unless otherwise specified. In by-visit summary tables, only scheduled visits/timepoints will be summarized.

Time to event data will be summarized using the Kaplan-Meier (KM) method, which will include the estimated median, 25th percentiles, 75th percentiles, and their 95% confidence interval (CI). The CIs will be calculated using a log-log transformation. The event-free probability and its 95% CI will be calculated at days 4, 8, 15, 22, 29, 60 and 90 as appropriate using Greenwood's formula with a log-log transformation.

The 95% confidence interval (CI) of the difference in the proportion (KPL-301 – placebo) will be primary based on Cochran Mantel-Haenszel (CMH) test stratified by the randomization strata for binary (proportion or rate) endpoints.

All relevant subject data will be listed by cohort, treatment, subject and visit/time point including both scheduled and unscheduled visits.

Analyses of selected Day 90 efficacy endpoints will be conducted in the Day 90 analysis set in the Day 29 database lock. All Day 90 efficacy endpoints will be analyzed based on the ITT analysis set at the Day 90 database lock.

#### **4.1. Randomization, Stratification, and Blinding**

An Interactive Web Response System (IWRS) will be used for assignment of the subject identification number at enrollment, randomization to a treatment arm (10 mg/kg KPL-301, 6 mg/kg KPL-301 or placebo), and assignment of blinded investigational product.

The randomization is stratified by the three following characteristics for subjects in Cohort 1 and by the first two following characteristics for subjects in Cohort 2:

1. Use of approved standard of care antiretroviral therapy: yes vs. no
2. Age: <65 vs.  $\geq 65$  years
3. Acute respiratory distress syndrome (ARDS) status: normal – mild ( $> 200$  PaO2/FiO2) vs. moderate-severe ( $\leq 200$  PaO2/FiO2). If PaO2 is unavailable, use SpO2/FiO2: normal–mild ( $>235$ ) vs. moderate-severe ( $\leq 235$ )

There should be no overlap of subject populations between the two cohorts since Cohort 1 baseline NIAID should be 3 or 4 and Cohort 2 baseline NIAID should be 2. In case of subjects being erroneously randomized under the incorrect cohort, the subjects will be analyzed in the correct cohort defined by the baseline NIAID scale. Subjects with baseline NIAID  $\geq 5$  will be included in Cohort 1 for the ITT and safety populations but excluded from Cohort 1 in the per-protocol analyses.

If subjects were randomized based on incorrect baseline information for use of approved standard of care antiretroviral therapy and age, then the correct strata will be used for stratified analysis rather than the incorrect strata in the IRT.

For ARDS status, data collected in IRT will be used since actual ARDS status at randomization was not collected in EDC. For Cohort 1 subjects who were incorrectly randomized under Cohort 2, the actual ARDS status derived from baseline information in EDC will be used, since the randomization for Cohort 2 is not stratified by ARDS status in the IRT.

If fewer than 5 subjects are in a stratification group of all three (or two for cohort 2) factors, that group will be pooled with another stratification group. If the same situation occurs, strata for the second factor will be pooled. If the same situation still exists, the analysis will be done without stratification.

For stratified analyses, if there is no event for both arms of comparison, or all responses are the same within a stratification group, that group will be pooled with another stratification group per the order of the stratification factors listed previously. This principal will be analogously applied to subgroup analyses.

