9	Tuberculosis screening is mandatory for South Africa sites and is at the discretion of the Investigator elsewhere. If required, one positive (or 2 indeterminate) interferon gamma release assay test results or one positive PCR test is exclusionary.
10	The NIAID score should be recorded at the time of randomization for all eligible subjects. For subjects in Cohort 1 only, also record 1) either PaO 2 (mmHg), if available, or SpO 2 (%), and 2) FiO 2 (%) for subjects on assistive ventilation or L/min of oxygen supplementation for subjects not on assistive ventilation (e.g., simple mask/cannula). Initiation of study drug administration should occur within 24 hours of randomization.
11	If the subject remains hospitalized after Day 8 these assessments should be collected daily until the day of discharge (ie, Days 9-14, 16-21, 23-28 or after Day 29). On Day 1, assessments should be collected at the time closest to and prior to the initiation of study drug administration. Daily collection guidelines after Day 1: collect assessment in the morning at approximately the same time each day and closest to the collection of the NIAID score assessment, except for respiratory parameters (see footnote #16)
12	If available, ECHO performed from 90 days prior to randomization through Day 90 will be collected (report only).
13	If discharged, these assessments must be performed via phone call at Days 15, 22, and 29.
14	The NIAID at discharge to home should reflect status immediately post-discharge (ie, either 7 or 8).
15	Collect ventilation supportive measures (eg, pronation, nitric oxide use, tracheostomy) received by subjects on mechanical ventilation; details in the Site Manual.
16	Respiratory function parameters will be recorded daily until the date of Discharge. Daily values based on the highest daily FiO 2 , including PaO 2 , FiO 2 , SpO 2 and oxygen requirement. Other arterial blood gas parameters if available should be recorded. In addition, other supportive measures including pronation, neuromuscular blockade, tracheostomy, ECMO, vasopressor or inotropic therapy, inhaled nitric oxide or other should be recorded.

Global Version 6 (Amendment 5)

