### **3. ANALYSIS SETS**

#### **3.1. Intent-to-Treat (ITT) Analysis Set**

All randomized subjects will be included in the ITT analysis set. All efficacy analyses of the study will be based on the ITT analysis set. All ITT analyses will be based on the randomized treatment.

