#### **5.7.2. NIAID Scale and Missing Data Imputation for Binary Endpoints**

NIAID scores at randomization should be derived from the last NIAID assessment prior to randomization. When not able to be derived, the screening NIAID will be used unless missing, in which case the (first) score from Day 1 will be used.

Baseline NIAID scores should be derived from the last NIAID assessment prior to dosing.

When two or more NIAID scores are collected on the same study day, the lowest score will be used, except at the date of discharge, in which the highest NIAID score will be used. When the derived NIAID at randomization happens to be from Day 1, then the Day 1 NIAID should be the lowest score on or after the NIAID at randomization time.

For endpoints where the event of interest is favorable, like proportion of subjects alive and free of ventilation, and proportion of subjects with 1-point/2-point clinical improvement, the following imputation rule of NIAID scale will be adopted:

- When the NIAID assessment is missing at the target day (Day 15, 29, etc.), the NIAID score closest to and within the window of the target day will be used. In case of ties with equal number of days on either side of target day, the value before the target day will be used. The window is (-2 days, +2 days) for Day 15 endpoints, (-2 days, +4 days) for Day 29 endpoints, and (-7 days, +14 days) for Day 90 endpoints.
- When no NIAID assessment is available within the window of the target day, the primary treatment comparison will be based on a combination of responder imputation and non-responder imputation. The rules taking into consideration of missing data are mostly related to subjects being improved and discharged from the hospital.
  - Discharged subjects will be considered as having had the event (responders).
  - Subjects who are still in the hospital will be considered as not having had the event (non-responders).
  - Subjects who died will be considered as not having had the event for all subsequent target days after discontinuation (non-responders).

- Subjects who terminated study before the target day, if the NIAID met the endpoint criteria as of last assessment before the study termination, they will be considered as having had the event for all subsequent target days after discontinuation (responders).
- Subjects without any post randomization assessment will be considered non-responders.

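### Phase 3 SAP 4.1 settles a misrandomized subject's cohort by a pre-dose NIAID score that can post-date randomization

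*Combined protocol and SAP*

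**What the plan says.** Phase 3 SAP 4.1 expects no overlap between cohorts because "Cohort 1 baseline NIAID should be 3 or 4 and Cohort 2 baseline NIAID should be 2". It then gives a correction rule with a trigger, "In case of subjects being erroneously randomized under the incorrect cohort", and a remedy, "the subjects will be analyzed in the correct cohort defined by the baseline NIAID scale". Subjects with a baseline score of 5 or more are placed in Cohort 1 for the ITT and safety sets on the score alone, with no reference to an error.

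Phase 3 SAP 5.7.2 defines two scores:

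- For baseline: "Baseline NIAID scores should be derived from the last NIAID assessment prior to dosing".
- For randomization: "NIAID scores at randomization should be derived from the last NIAID assessment prior to randomization". If this cannot be derived, the screening score is used, and failing that the first Day 1 score.

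The cohort rule uses the first and not the second.

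The protocol's Schedule of Activities (footnote 10) says "The NIAID score should be recorded at the time of randomization for all eligible subjects" and "Initiation of study drug administration should occur within 24 hours of randomization". Footnote 11 asks for Day 1 assessments as close as possible before the infusion starts.

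Phase 3 SAP 3.1 states "All randomized subjects will be included in the ITT analysis set", by randomized treatment. It does not say whether cohort is also as randomized. SAP 5.7.1 plans no formal testing in Phase 3 Cohort 2.

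**The concern.** Cohort decides which primary endpoint applies to a subject and whether the subject enters a confirmatory test at all, so it should be fixed by information available at randomization. Here the score that settles it may be taken up to a day later, in patients whose respiratory status can change within hours.

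The SAP never says how to recognize an erroneous randomization, other than by a baseline score that does not fit the cohort. A programmer who finds a Cohort 1 subject with baseline NIAID 2 could take that as the error. If the subject was randomized correctly and intubated before the infusion, the move would take a post-randomization deterioration out of the tested cohort. Yet SAP 5.7.3 starts the ventilation-free-survival clock at randomization, so the same intubation is already an event for that secondary endpoint. Under the same reading, a Cohort 2 subject extubated before dosing would enter Cohort 1.

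There is also a narrow gap. An undosed subject who was in fact misrandomized has no pre-dose score for the rule to use. SAP 4.2.2 sets Day 1 to the randomization date for undosed subjects but gives no matching rule for baseline NIAID.

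**Working it through.** **Can the classifying score fall after randomization?** Yes, whenever a NIAID score is taken between randomization and the infusion. Footnote 11 plans a pre-infusion Day 1 score, and footnote 10 allows up to 24 hours between the two. If no score is taken in that interval, the baseline and randomization scores coincide.

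**What happens to a subject randomized to Cohort 1 at NIAID 3 or 4 and intubated before dosing?** NIAID at randomization is 3 or 4 and baseline NIAID is 2. On the literal trigger, the subject was not randomized in error and stays in Cohort 1. On the score-based reading, the subject moves to Cohort 2.

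**The design figure.** Inputs from SAP 1.4: 87.5% and 74.4%, 200 per arm, two-sided alpha 0.05, 581 randomized in 1:1:1 allocation (581/3 = 193.7 per arm).

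Power = Φ{[|p1 − p2|√n − 1.96√(2p̄(1 − p̄))] / √(p1(1 − p1) + p2(1 − p2))}, with p̄ = 0.8095.

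- n = 200: (1.853 − 1.088)/0.548 gives 91.9%, which agrees with the stated minimum of 90%.
- n = 193.7: 91.0%.

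**Effect of balanced removal.** The share f intubated between randomization and dosing is not in the documents; 0.5% to 5% is assumed. All such subjects are treated as non-responders within the design rates, which is the least favourable case. After removal each rate becomes p/(1 − f) and each arm n(1 − f).

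| Assumed f | Removed per arm | Active | Placebo | Difference (points) | Power |
|---|---|---|---|---|---|
| 0 | 0 | 87.5% | 74.4% | 13.1 | 91.0% |
| 0.5% | 1.0 | 87.9% | 74.8% | 13.2 | 91.6% |
| 1% | 1.9 | 88.4% | 75.2% | 13.2 | 92.2% |
| 2% | 3.9 | 89.3% | 75.9% | 13.4 | 93.3% |
| 5% | 9.7 | 92.1% | 78.3% | 13.8 | 96.4% |

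At 1-2% this is 0.01 × 581 to 0.02 × 581, or about 6 to 12 subjects over three arms.

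**Effect of chance imbalance.** Pooled two-sample z test, 194 per arm, non-responders removed from one arm only:

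- 159 against 144 responders: p = 0.066 with all kept; p = 0.040 if two leave the active arm (159/192 against 144/194).
- 160 against 144: p = 0.049 with all kept; p = 0.060 if one leaves placebo (160/194 against 144/193).
- For contrast, 159 against 144 with four removed from each arm gives p = 0.056, on the same side of 0.05 as before.

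These are unstratified illustrations at the 0.05 level. Under the Hochberg rule in SAP 5.7.1 the operative level may be 0.025, depending on the other dose.

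**The case against.** The strongest reply is that the rule has a trigger. It applies only to subjects randomized in error, and a patient who deteriorates after a correct randomization is not one. The neighbouring paragraphs of SAP 4.1 also concern mistakes: wrong baseline information for the strata, and subjects incorrectly randomized under Cohort 2. This stands as the literal reading, so the text cannot be said to order the removal. It does not close the point, because the only stated marker of an error is the baseline score and the adjacent rule for scores of 5 or more works on the score alone.

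The second reply also stands. Deterioration before a blinded infusion cannot be caused by study drug, so expected removal is equal across arms and does not by itself inflate Type I error. The reversals shown above need both a result at the boundary and one-sided removal.

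A reader might go further on three matters that the documents do not support:

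- **That the subjects removed are certain primary-endpoint failures.** SAP 5.7.2 scores status at or near Day 29 and counts discharged subjects without a score in the window as responders, so a subject intubated early and later discharged could count as a success. Protocol 10.1.1 points the other way by counting anyone who has met a score of 2 as ventilated. The Phase 3 SAP's own endpoint section is not legible in the text available.
- **That the rule reverses the ITT definition revised on FDA guidance in SAP version 2.0.** A moved subject remains in the ITT set under the randomized treatment. What changes is the cohort, which that definition does not address.
- **That every undosed subject lacks a cohort.** Cohort comes from randomization, and the score is consulted only for misrandomized subjects.

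**Conclusion.** The point holds as an ambiguity in a rule that governs membership of the confirmatory cohort. The score named to settle cohort can post-date randomization, a score tied to randomization is already defined, and no text protects a correctly randomized subject from being sorted by the later one. Removal of pre-dose intubations from Cohort 1 is a plausible way to program the rule, not what it plainly says.

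The expected effect is small. At an assumed 1-2% affected, the design difference rises from 13.1 to about 13.2-13.4 points and power from 91.0% to 92.2-93.3%; at 5% the difference is 13.8 points. These figures assume equal shares in both arms and that every removed subject would have been a non-responder. The remaining exposure is a departure from analysis by cohort as randomized, and the possibility that one or two unevenly distributed subjects decide a borderline result. The change is still worth making because it costs little and removes a discretionary choice from the primary analysis.

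**What to change.** In Phase 3 SAP 4.1, before database lock:

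1. Define the correct cohort by NIAID at randomization as in SAP 5.7.2, in place of baseline NIAID. This also covers undosed subjects.
2. Move a subject only if the recorded status at randomization contradicts the assigned cohort.
3. Keep the IWRS cohort where only a fallback score (screening or first Day 1) is available. Screening may be up to 3 days before randomization, and Cohort 2 requires ventilation started within the preceding 48 hours. A subject correctly randomized to Cohort 2 could therefore carry a screening score of 3 or 4.
4. State that NIAID changes between randomization and dosing do not change cohort.
5. Add a sensitivity analysis of the primary and secondary endpoints by IWRS cohort as randomized.

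The cost is a few sentences and one additional set of tables, since the variable is already derived. There is one small limitation. The protocol's summary of changes shows that recording NIAID at the time of randomization entered the global protocol with Version 5, so subjects enrolled earlier would rely on the last pre-randomization score or on the IWRS cohort.

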## **4.2. Data Analysis General Information and Definition**

### **4.2.1. Study Drug**

Study drug or study treatment refers to 10 mg/kg KPL-301 (mavrilimumab), 6 mg/kg KPL-301 (mavrilimumab) or placebo.

### **4.2.2. Day 1**

**Day 1** is defined as the day of the study treatment after randomization.

For subjects without dosing, Day 1 is defined as the randomization date in the analysis of efficacy while endpoints points are defined by study day, like Day 29, Day 90 endpoints.

### **4.2.3. Baseline Values**

Baseline is defined as the last non-missing value obtained prior to the start of study treatment. The baseline NIAID is defined separately in Section [5.7.2](#).

The change from baseline values will be derived for each subject as the post-baseline evaluation minus the baseline evaluation.

#### **4.2.4. Last Contact**

Last contact or last date known alive is defined as the last non-imputed date of any subject record prior to or on the data cut-off date in the clinical database.

#### **4.2.5. Calculation Using Dates**

Calculations using dates will adhere to the following conventions:

Study day for a date of interest (TARGET DATE) is calculated as

STUDY DAY = TARGET DATE – Date of Day 1 + 1 if TARGET DATE is on or after Day 1;

STUDY DAY = TARGET DATE – Date of Day 1 otherwise.

Day X in this document refer to the study day X, where X can be 4, 8, 15, 22, 29, 60, 90, etc.

#### **4.2.6. Duration Derivation**

Unless otherwise specified for a specific panel or variable, duration variables will be derived according to the following rules. Duration variables expressed in units greater than day will be rounded to 1 decimal place.

Duration (in days) = [end date – start date +1]

Duration (in weeks) = [end date – start date +1] / 7

Duration (in months) = [end date – start date +1] / 30.4375

### **4.3. Windowing of Visits**

Data will be summarized by eCRF scheduled visits and allowed visit windows. When there are multiple assessments for a scheduled visit, the first non-missing value will be used. No additional windowing will be considered.

Due to changes of visit windows across protocol versions, the minimum window that can cover windows in all protocol versions will be used in the analysis of the efficacy endpoints: the window is (-2 days, + 2 days) for Day 15 endpoints, (-2 days, + 4 days) for Day 29 endpoints, (-7 days, +14 days) for Day 90 endpoints.

### **4.4. Methods for Handling Missing Data**

For efficacy data, missing NIAID scale and survival status at target days will be handled per Section 5.7.2.

For safety data, refer to Section 8.1 for detailed date imputation guidelines.

### **4.5. Protocol Deviations**

The study team will have a blinded review of protocol deviations to determine their classification (important, not important) periodically. Prior to the database lock, the study team will assess impact of all important protocol deviations on efficacy and whether they should be excluded from per-protocol analysis set.

The number of important protocol deviations, the number of subjects with at least one important protocol deviation, and the number of subjects with at least one important protocol deviation with/without a potential impact on efficacy will be summarized by treatment group. The protocol

deviation criterion types will also be summarized, with reference to an evaluability document that will be signed off prior to database lock.

All protocol deviations will be presented in by-subject listings, and subjects with protocol deviations that lead to exclusion from the per-protocol analysis set will be flagged.

#### **4.6. Data Cut-off Date**

Two DBLs are planned for Phase 3 Cohort 1:

- For the first DBL, unless otherwise specified, all analyses will be conducted based upon data through Day 29 for each subject instead of a fixed data cut-off date:
  - For Day 29 efficacy endpoints, a + 4-day window is allowed.
  - For Day 90 efficacy data, mortality rate will be produced.
  - Selected TEAE tables may be produced for a subgroup of subjects (for selected sites and randomization date) with complete TEAE data through Day 90.
  - Laboratory endpoints will only be analyzed for baseline values.
- For the second DBL, all analyses will be updated based on the complete study data. Data throughout Day 29 are expected to remain the same as the first DBL.

Only one DBL is planned for Phase 3 Cohort 2. All data through study completion/early discontinuation will be included.

## **5. STATISTICAL METHODOLOGY**

### **5.1. Study Population**

A summary of analysis sets by treatment will be presented along with percentages relative to the ITT Analysis Set.

- ITT Analysis Set
- Safety Analysis Set
- Per-protocol Analysis Set
- Day 90 Analysis Set

A listing will be provided to describe when informed consent was obtained and if the subject meets all inclusion/exclusion criteria. Reasons of subjects' exclusion from safety, or PP analysis sets will also be listed.

### **5.2. Subject Disposition**

The number and percentage of subjects will be tabulated for the ITT analysis set by treatment:

- Subjects who are ongoing
- Subjects who completed the study
- Subjects who ended study early

Reasons for early study discontinuation will be summarized with the following categories:

- Adverse event
- Lost to follow-up
- Death
- Physician decision
- Site terminated by sponsor
- Study terminated by sponsor
- Technical problem
- Withdrawal by subject
- Other

A listing will be presented to describe whether the subject is on study, completed the study, date of completion or early withdrawal, and the reason for early study discontinuation.

